[figure not shown]

## 1. SPECIFIC AIMS

The purpose of this pilot clinical study is to test a methodology for using imaging by CT offered through the Advanced Multimodality Image Guided Operating (AMIGO) to guide an excisional biopsy of lung abnormalities identified by CT scans.

Our hypothesis is that an effective marking strategy of 3cm or smaller lung lesions, using intra-operative imaging-guidance, will enable accurate and efficient lesion resection while preserving as much as possible of the normal lung parenchyma by limiting the resection to the lesion and its immediate surrounding.

Our clinical initiative has 2 specific aims, one primary major and the other secondary taking advantage of this design:

**Aim 1:** To determine the feasibility of image guided VATS (Video Assisted Thoracoscopic Surgery) resection using real-time anatomical imaging modality for lung lesions/nodules. Specifically, we seek to establish the flow of the procedure and to determine the morbidity, success rate (as defined by complete resection), time from incision to closure of each procedure and radiation dose used in each procedure.

**Aim 2:** to determine whether molecular analysis of the lesion/nodule in conjunction with cytological analysis using FNAs (Fine Needle Aspirations) just prior to resection can predict diagnosis and prognosis.

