Screening with computed tomographic (CT) scans has to some degree changed the technologies available for surgery for both lung cancers and for benign diseases. In the past and for most cases in the US currently (>75%), most lung cancers were relatively large and subjects required open thoracotomy for resection. Now-a-day, many cancers are much smaller and can be accessed through minimally invasive approaches, Video Assisted Thoracic Surgery (VATS) [10]. This is particularly the case in specialized centers such as BWH where most Thoracic Surgeons will attempt VATS resection for the majority of pulmonary nodules for any etiology. The same applies to non-cancerous nodules that need to be biopsied or resected for diagnosis and/or treatment. This surgery is routinely performed through 3 small incisions (1cm or so each) whereby one incision is used for the placement of a rigid video telescope camera and the other incisions are used to grab and mobilize the lung, bring it closer to one incision which will allow palpation of the lung with a finger tip

CONFIDENTIAL

This document is confidential. Do not disclose or use except as authorized.

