to identify the nodule/lesion that will then be cut out using a stapling device. We recently reviewed (unpublished results submitted for publication) all subjects aged 21-85 years who had surgical resection for small ( $\leq 2\text{cm}$ ) non-small cell lung cancer at BWH from 2004-2008. Of 347 subjects, 10.1% experienced  $\geq 1$  major complication and 16.1% a hospital stay of  $\geq 1$  week. The complications included: Adult respiratory distress syndrome (1), Aspiration (1), Bronchopleural fistula (1), Cerebro vascular accident (1), Empyema (1), Myocardial infarction (1), Pulmonary edema (1), Pulmonary embolism (1), Ventilator for more than 7 days (1), Wound infection (1), Chylous leak (2), Tracheostomy (2), Acute renal failure (3), Atrial fibrillation (4), Re-operation due to bleeding (4), Re-intubation (5), Pneumonia (7), Air leak for at least 7 days (20). Of interest we also found that for a 30-minute increase in operative time, the odds of  $\geq 1$  major complication are estimated to increase by 103% (OR 2.03; 95% CI: 1.45-2.84), supporting the need to reduce operative time with a strategy such as proposed in this protocol. Though these complications and rates are only representative of one specific subset of our subjects they provide a highly relevant snap shot of rates and types of complications expected in this protocol.

**The crux of the challenge and the reason for this protocol is that at surgery, many of these nodules/lesions are hard to palpate and to precisely define their location for resection.** This is particularly true for smaller nodules or GGOs, precisely the ones that require resection to provide early diagnosis and therapy since at least half may be benign. Thus, using current technologies, which are non-image guided, result in three potential non-ideal outcomes: 1. A more extensive resection of normal lung parenchyma (such as lobectomy or segmentectomy) to make sure that the lesion is included even if it is non-palpable; 2. An enlargement of at least one incision to insert the hand into the chest for better physical definition-resulting in a more painful and complex recovery for the subject with resulting longer recovery, chronic pain and greater cost; 3. Too close a surgical margin to the cancer requiring re-operative surgery of increasing the chance of recurrence.

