Our goal in this protocol is to enroll subjects who require VATS for specified lung lesions, have the subject be operated in the AMIGO suite where they undergo the following process: intubated with a double lumen tube, positioned in the lateral decubitus position, undergo CT- to confirm the location of the nodule, perform image guided needle biopsies and mark the lesion by placing a needle guided hookwire and/or T-bar. At this point, VAT surgery will be performed to resect the lung lesion utilizing the marking, which will remove the hookwire and/or T-bar with the specimen. The specimen will then be removed in an Endo-bag and submitted for a quick CT picture (away from the subject) and sent for pathological analysis. Only the underlined elements are experimental, the operation itself and indications are standard of care. The intentions are to define the methodology, risks, exposure etc. and then work in follow-up trials to potentially improve upon the marking device and the procedure to get them to the point where this approach is available for any subject undergoing lung resection. We believe that this is a game changing approach that is long overdue for thoracic surgery.

The second aim of this proposal takes advantage of the design of the protocol. In addition to placing an image guided marker, we propose to also obtain FNA from the lesion to be used for both cytological and molecular analysis. The results supporting this proposed aim come from our laboratory where through NCI funded projects we developed molecular tests based on gene expression strategies to distinguish normal lung from lung cancer [18] and mesothelioma from other cancers. We currently have a separate open clinical trial (with IRB approval) to obtain FNA biopsies under image guidance with ultrasound in subjects with mesothelioma (DFCI IRB protocol number 04-349). To-date about 115 subjects underwent this procedure with no complications [19].

The genetic analysis for this protocol involves taking the specimens obtained during the FNA procedure and using the RNA from these specimens to make cDNA. This cDNA will be used for transcriptional profiling and RNA sequencing. This will be done both in the tumor specimen as well as the adjacent normal specimen.

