Each device is connected by a suture to the outside of the chest wall to allow constant guidance. Also, by visualizing the tract of the suture one can see where it enters the lung. Depending on the extent and location of the lesion one or two such devices may be placed (if needed to encompass the borders of the lesion). Once the device is placed, standard video assisted lung surgery will commence using 3-4 incisions, rigid video telescope camera and fluoroscopy if needed will guide the localization of the nodule. The lung around the nodule will then be grasped and resected with the hookwire and/or T-bar within it. The specimen will be then removed, investigated with imaging (away from the subject to avoid unnecessary radiation) to confirm that the original lung nodule/lesion is within and then taken to pathology to confirm that an abnormal nodule was resected and that the margins are appropriate, following our standard of care. The operation will then proceed and be concluded per standard of care.

**Picture 1, 2:** Metallic Hookwire that can be tracked with imaging. In picture 1:

CONFIDENTIAL

[figure not shown]
This document is confidential. Do not disclose or use except as authorized.

Human lung specimen (staples in the perimeter of the biopsy)- the tip of the Kopan's wire is market with red arrow

Picture 1

[figure not shown]
In picture 2: Wire in a breast tissue.

Resected Breast specimen radiograph with  
Kopan wire in it

Picture 2

In picture 3 and 4: Metallic T-bar that can be tracked with imaging.

**For Aim 2:** to determine whether molecular analysis of the nodule in conjunction with cytology using Fine Needle Aspirations FNAs can predict diagnosis and outcome. Aim 2 is based on preliminary work from our group showing that molecular analysis of FNA from thoracic lesions can provide accurate diagnosis. Since the subject will be in a position under general anesthesia to undergo needle placement of the hookwires and/or T-bar, we request permission for two more needle passes prior to it to obtain material for cytology and molecular testing to determine the diagnostic accuracy of combining the two. This is based on an approved protocol (DFCI 04-349 FINE NEEDLE BIOPSIES IN MPM) for which over 100 subject have been enrolled with no complications and diagnostic accuracy for mesothelioma of 93%. We anticipate that in this setting there should not be added risk to the subject .

Study endpoint: morbidity rate, 25subject .

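### Aim 1's success rate counts complete resection only, so it does not register marking failures that are rescued by a larger incision, conversion or wider resection

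*Combined protocol and SAP*

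**What the plan says.** Section 1 (Specific Aims) hypothesises that an effective marking strategy will allow accurate and efficient resection while "preserving as much as possible of the normal lung parenchyma by limiting the resection to the lesion and its immediate surrounding". Aim 1 then lists what will be determined, including morbidity, radiation dose and "success rate (as defined by complete resection), time from incision to closure of each procedure". Neither Section 5 nor Section 6 adds to this definition of success.

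Section 2 (Background) gives three unwelcome results of surgery without image guidance:

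1. "A more extensive resection of normal lung parenchyma (such as lobectomy or segmentectomy) to make sure that the lesion is included"
2. "An enlargement of at least one incision to insert the hand into the chest"
3. "Too close a surgical margin to the cancer requiring re-operative surgery"

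The same section describes fingertip palpation as part of routine VATS: the lung is mobilised to "bring it closer to one incision which will allow palpation of the lung with a finger tip".

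The intended use of the marker appears in two places. Section 2 says that "VAT surgery will be performed to resect the lung lesion utilizing the marking", and Section 5 (For Aim 1) says "The lung around the nodule will then be grasped and resected with the hookwire and/or T-bar within it". Section 5 also has the specimen imaged to confirm that it contains the nodule, and has pathology check the margins.

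Section 5 names morbidity as the study endpoint. Section 6 contains one decision rule, on major complications (3 or fewer of 25), and no target or analysis for the success rate.

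**The concern.** The hypothesis is about the marking; the success definition is about whether the lesion came out. The two separate whenever marking fails and the surgeon still removes the lesion by another route. The first two unwelcome results in Section 2 are such routes: their purpose is to find or include the lesion, so both can end in complete resection.

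The pilot exists to test a methodology, and Section 2 plans follow-up trials to improve the marking device and the procedure. Those trials will need to know how often the marked route was actually completed. A success rate that reads the same whether the marker guided the resection or the surgeon had to work around it gives them only part of that.

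**Working it through.** **The plan's own figures.** For the rule of 3 or fewer major complications in 25, exact binomial probabilities are P(X ≤ 3 | 25, 0.10) = 0.7636 and P(X ≤ 3 | 25, 0.25) = 0.0962. These reproduce the 76% and 10% in Section 6. They concern morbidity, and nothing below changes them.

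**How each route scores under the literal definition.**

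| Course of the case | Scored as success? |
|---|---|
| Marker guides VATS resection, lesion fully out | Yes |
| Marking fails, incision enlarged or case converted, lesion fully out | Yes |
| Marking fails, lobectomy or segmentectomy done to include the lesion | Yes |
| Marking fails, nodule missed or margin inadequate | No, on a reasonable reading |

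So two of the three unwelcome results in Section 2 can score as success, and the third counts against it. Section 8 lists three expected benefits: less parenchyma removed, shorter operating time, and staying VATS. Only operating time is a named Aim 1 measure.

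**How strongly the rate tracks marking.** Let m be the share of cases in which the marker guided a complete resection, and r the share of the remaining cases still completely resected by another route. Then

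complete resection rate = m + (1 − m) × r.

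The documents give neither m nor r, so both are assumed over a range:

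| r | m = 50% | m = 70% | m = 90% |
|---|---|---|---|
| 0 | 50% | 70% | 90% |
| 0.5 | 75% | 85% | 95% |
| 0.9 | 95% | 97% | 99% |
| 1.0 | 100% | 100% | 100% |

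For example, 0.70 + 0.30 × 0.9 = 0.97. At r = 0 the rate equals m; at r = 1 it carries no information on m. At r = 0.9 the whole span from m = 50% to 90% covers 4 points (95% to 99%). In 25 subjects that cannot be resolved: 24/25 has an exact 95% CI of 79.6–99.9%.

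**What a second rate would show in 25 subjects.** Assume that all 25 have marker placement attempted, all lesions are completely resected, and k cases are rescued. Complete resection is 25/25 for every k; marker-guided success is (25 − k)/25. Intervals are Clopper-Pearson 95%.

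| k | Complete resection | Marker-guided success |
|---|---|---|
| 0 | 100% (86.3–100%) | 100% (86.3–100%) |
| 1 | 100% (86.3–100%) | 96% (79.6–99.9%) |
| 3 | 100% (86.3–100%) | 88% (68.8–97.5%) |
| 5 | 100% (86.3–100%) | 80% (59.3–93.2%) |

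The chance of seeing at least one rescued case is 1 − (1 − p)^25. For assumed true rescue rates p of 2%, 5%, 10% and 20% this is 39.7%, 72.3%, 92.8% and 99.6%. If none is seen, the exact two-sided 95% upper limit for the rescue rate is 1 − 0.025^(1/25) = 13.7%. The trial is large enough for the second rate to be worth reporting.

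**The case against.** The strongest reply is that the success rate does not stand alone. Aim 1 also sets out to establish how the procedure runs, and to measure time and dose. The rate belongs to image-guided VATS, which Sections 2 and 5 describe as resection using the marking with the marker in the specimen, so a converted case could be read as not completed. Section 6.1 collects the discharge summary, coded procedures, pathology and radiology.

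Part of this stands. The alternative reading is possible, and the records would show much of what happened. But the procedural objective has no defined measure, the marker text describes a step and not a criterion of success, and time does not reveal its cause. No item named in Section 6.1 records how the nodule was localised or why a resection was enlarged. Coded procedures could show a lobectomy without its reason.

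Three stronger readings are tempting, and the documents do not support them:

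- *The rate says nothing about whether marking worked.* It does fall when failed marking leaves a missed nodule or an inadequate margin, and Section 5 checks for both.
- *Any palpated nodule is a marking failure.* Section 2 presents palpation as routine technique, and it is not among the three unwelcome results. Feeling a marked nodule does not show that the marker failed.
- *The trial's conclusion is undermined.* The formal endpoint is morbidity, and the success rate has no threshold and drives no decision.

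**Conclusion.** The concern holds in a limited form. The complete resection rate is insensitive to rescued marking failures and so only partly informs the marking hypothesis. This follows from the wording of the definition and needs no assumption about how often markers fail. The numerical size does: each rescued case lowers a marker-guided rate by 1/25, or 4 points, and leaves the present rate unchanged, but the documents give no figure for how many to expect. The illustrations show what could be hidden; they do not predict that markers will fail. The effect is confined to the descriptive feasibility conclusion. The change is worth making because it is cheap and lets the pilot report on its own question.

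**What to change.** Keep the complete resection rate. Add to Aim 1 and Section 6 a descriptive **marker-guided success rate**, specified as follows:

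- **Success:** complete resection by VATS, with the nodule and at least one marker in the first specimen, and no enlarged incision, conversion, or lobectomy or segmentectomy needed to find or include the lesion. One marker is enough, because Section 5 allows one or two devices.
- **Not a failure:** extension of the resection because of the pathology diagnosis.
- **Palpation:** report descriptively. Count it as a failure only when the marker was dislodged or did not guide the resection.
- **Denominator:** all subjects in whom marker placement was attempted.
- **Reporting:** both rates with exact 95% CIs, and the reason for each case in which they disagree.

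Add two fields to Section 6.1, completed by the surgeon at the end of the case: how the nodule was localised (marker, imaging, palpation), and why any incision or resection was enlarged. Whether the nodule and marker are in the specimen can be read from the specimen imaging already planned.

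The cost is two fields per subject, with no extra subjects or imaging and no change to the decision rule. The downsides are some surgeon judgement about intent and a second rate that may be lower than the first. With no control arm, the new rate describes how often the marked route was completed; it cannot show that marking is better than palpation.

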## 2. BACKGROUND

Approximately 1,000,000 lung nodule and other abnormal lesions such as GGO (ground glass opacities) are detected in people in the United States each year. Lung nodules are found on 1 in 500 chest x-rays, and 1 in 100 CT scans of the chest. In reported studies, up to 51% of smokers aged 50 years or older have pulmonary nodules/lesions on CT scans.

A solitary pulmonary nodule is defined as a discrete, well-margined, rounded opacity less than or equal to 3 cm in diameter that is completely surrounded by normal lung parenchyma, does not touch the hilum or mediastinum, and is without associated atelectasis or pleural effusion. GGO (Glass Ground Opacity) refers to specific changes in the lung parenchyma on CT that may represent tumor, pre-malignant lesion or other benign lung lesions.

Whether detected serendipitously or during a routine investigation, solitary pulmonary nodules/lesions pose a challenge to both clinicians and subjects[1]. A nodule on a chest radiograph raises several questions: Is the nodule benign or malignant? Should it be investigated or observed? Should it be surgically resected? The clinical context is also important and includes age, history of immunodeficiency (inherent or due to disease, chemoradiation, diabetes), travel history in endemic area for specific pulmonary pathogens (Ohio River valley, San Joaquin Valley, TB endemic areas), current infectious symptoms etc. In different clinical

CONFIDENTIAL

This document is confidential. Do not disclose or use except as authorized.

circumstances the lesions/nodules can represent specific infections, benign growth, cancers or intrinsic pulmonary abnormalities.

Most solitary pulmonary nodules are benign. Seventy five percent of nodules less than 2 cm are benign [2] but they may represent an early stage of lung cancer. Lung cancer survival rates remain dismally low at 16% at 5 years [3,4]. If detected early enough, lung cancer can be treated and survival chances improved [5,6]. Early lung cancer, when the primary tumor is less than 3 cm in diameter (stage 1A or 1B), may lead to 5-year survival rates as high as 70-80%, yet only 15% of lung cancers are diagnosed at this early stage [3]. Likewise, a benign diagnosis can relieve patients from the radiation burden of follow up with CT scans and in some cases can provide a life saving treatment with steroids, antibiotics etc.

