### **3. Participant SELECTION**

#### **Subject Selection:**

This study will be initially limited to subjects with lung nodules or lesions 3cm or smaller in the outer half portion of the lung/lobe and who are candidate for VATS at

CONFIDENTIAL

This document is confidential. Do not disclose or use except as authorized.

DFCI or BWH and consent for the procedure. The subjects will be formally consented at BWH only. The subjects may initially be told about the research procedure during a visit at DFCI with their thoracic surgeon, but if they choose to participate in the trial they will be consented at BWH. The CT will be reviewed by the study radiologist and thoracic surgeon prior to enrollment. At least 25 subjects scheduled for lung resection surgery will be enrolled to the study. The goal is 25 subjects who are enrolled into the trial.. All subjects will be chosen from the outpatient clinic of Thoracic Surgery, BWH.

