### **3.1 Eligibility Criteria**

Participants must meet the following criteria on screening examination to be eligible to participate in the study:

- **Subjects Procedures** – subjects who are candidate for VATS and were consented for the procedure will be eligible for enrolled to the study.
- **Measurable Nodule** – lesions that are nodules/GGO or other abnormal opacity that can be accurately measured in at least one dimension with longest diameter <= 30 mm using conventional techniques.
- **Nodule Location** - lesions that are located in the outer half portion of the lung/lobe.
- **Enrolment Site** – Subjects who are seen at BWH and or DFCI Thoracic Surgery outpatient clinics. However, the subjects will formally consented at BWH only.
- **Age** – Enrollment at Partners will be limited to adults, 18 years and older.
- **Number of subjects** = 25 subjects will be enrolled to this stage of the study. Adult subjects, non-pregnant, non breast feeding to avoid radiation exposure. Urine and/or blood pregnancy test will be obtained based on clinical indications.

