### 5.2 Duration of Follow Up

Participants will be followed after removal from study for 12 months.

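### Can 25 subjects followed for 12 months show whether needle-aspirate molecular analysis predicts prognosis, and must the plan change because they cannot?

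*Combined protocol and SAP*

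**What the plan says.** Section 1 calls the study a pilot with a primary and a secondary aim. Aim 2, the secondary one, is to determine whether molecular analysis of the lesion with cytology, on aspirates taken just before resection, "can predict diagnosis and prognosis". Section 5 restates the aim with a different last word: "can predict diagnosis and outcome". Neither prognosis nor outcome is defined.

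On size, section 3 (Subject Selection) asks for at least 25 subjects and adds "The goal is 25 subjects who are enrolled into the trial". Section 3.1 says "25 subjects will be enrolled to this stage of the study" and admits lesions "with longest diameter <= 30 mm using conventional techniques", without requiring malignancy. On follow-up, section 5.2 says "Participants will be followed after removal from study for 12 months".

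Section 6, the only statistical section, contains one rule: morbidity is acceptable if three or fewer of 25 subjects have a major complication. Section 5 names morbidity as the study endpoint. It also gives the additional needle passes a narrower purpose than the aim does, namely the diagnostic accuracy of cytology and molecular testing combined.

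**The concern.** The aim is worded as a question the trial will settle, with the same verb as the feasibility aim, and nothing labels the prognostic part exploratory. Many of these lesions will be benign, the malignant ones will mostly be small cancers, and follow-up is short, so deaths or recurrences will be very few. Read literally, the trial could report that a molecular profile does, or does not, predict prognosis on the strength of one or two events, and neither statement would be supported. Aim 2 is also the reason given for two extra needle passes under anaesthesia, so it matters what those passes can show.

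A second worry concerns the diagnostic half. Section 2 plans expression profiling and RNA sequencing of the specimens. A classifier chosen after seeing the pathology of 25 specimens would look more accurate than it is.

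**Working it through.** **Where the 25 comes from.** Section 6 states 76% power at a true complication rate of 10%, and a 10% chance of acceptance at 25%. With X binomial (n = 25):

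- P(X ≤ 3 | p = 0.10) = 0.764
- P(X ≤ 3 | p = 0.25) = 0.096

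Both stated figures reproduce. The size is justified by morbidity, and no figure is offered for Aim 2.

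**Inputs for Aim 2.**

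- Subjects: 25 (sections 3 and 3.1).
- Malignant share f: 25% to 50%. Section 2 gives 75% benign for nodules under 2 cm, and says at least half may be benign among the smaller lesions that need resection. It also expects a benign majority among people coming to surgical biopsy after screening. No figure is given for this cohort, so the range is an assumption.
- Five-year survival S: for early cancers section 2 says "may lead to 5-year survival rates as high as 70-80" per cent; for all stages, "Lung cancer survival rates remain dismally low at 16% at 5 years".
- Further assumptions: constant hazard, cancer deaths only, 12 months of observation in total.

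**Expected deaths.** One-year death probability q = 1 − S^(1/5); expected deaths = 25 × f × q.

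| S | q | f = 0.25 | f = 0.50 |
|---|---|---|---|
| 0.80 | 0.0436 | 0.27 | 0.55 |
| 0.70 | 0.0689 | 0.43 | 0.86 |
| 0.16 | 0.3069 | 1.92 | 3.84 |

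The chance of seeing no cancer death at all is (1 − f × q)^25. It is 0.76 at f = 0.25, S = 0.80, and 0.42 at f = 0.50, S = 0.70.

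**Stretching the assumptions.**

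- All five-year deaths moved into year one, early-stage survival: 25 × 0.25 × 0.20 = 1.25, to 25 × 0.50 × 0.30 = 3.75.
- Recurrence as the event, at an assumed 10-30% in one year: 25 × 0.25 × 0.10 = 0.63, to 25 × 0.50 × 0.30 = 3.75.
- Every lesion an early cancer: 25 × 0.0436 = 1.09, to 25 × 0.0689 = 1.72.
- Every lesion a cancer with all-stage survival: 25 × 0.3069 = 7.67. This contradicts the benign majority that section 2 expects, so it is not a realistic bound.

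**What so few events can show.** Suppose a two-group marker splits the subjects 12 and 13. If two deaths occur and both fall in the group of 12, the one-sided exact p is C(12,2)/C(25,2) = 66/300 = 0.22. With three it is 220/2300 = 0.096. By Schoenfeld's formula (two-sided 5%, 80% power, even split), a hazard ratio of 3 needs 4 × (1.96 + 0.84)² / (ln 3)², which rounds up to 27 events, more than the 25 subjects planned.

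**What the plan would do with them.** Nothing formal. Section 6 contains no prognostic test, cut-off, model or precision target, and no decision depends on one.

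**The diagnostic half.** Resected specimens go to pathology, so accuracy has a reference standard. As an illustration, 23 correct of 25 gives an exact 95% interval of 74% to 99%. That is wide but usable for a pilot.

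**The case for a change.** The strongest case for a change is that the labels do not rescue the wording. The pilot in section 1 is a test of the imaging method, nothing there or in section 5 marks prognosis as exploratory, and the aim supports a research procedure on patients. Softening the verb would cost a few words, so there is little reason to leave it.

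Much of this stands. The verb is too strong, prognosis is undefined, and no plausible input rescues the event count. Small departures in the inputs do not help either: section 3 allows somewhat more than 25 subjects, and section 5.2 leaves it unclear when the 12 months start.

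What does not stand is the consequence. The feared over-claim would have to come from an analysis that the plan does not contain. The specific reason section 5 gives for the needle passes is diagnostic accuracy, which the study can estimate. Treating prognosis as death or recurrence is also the reviewer's reading, because the text names neither.

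The classifier worry is speculative. Section 2 says the group has already developed gene-expression tests, and section 5 rests Aim 2 on that preliminary work. No passage says that a classifier will be picked after linkage to pathology. None says that it is locked either, but that silence is not evidence of a biased procedure.

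**Conclusion.** The arithmetic behind the concern is right, but it does not call for a change. About 0.3 to 0.9 cancer deaths are expected with early-stage survival, and at most 3.8 with all-stage survival. This assumes 25 subjects, 25-50% malignant, a constant hazard, cancer deaths only and 12 months of observation. Any prognostic result can therefore only be descriptive.

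Low power for a secondary aim of a pilot is a fair trade-off when the plan claims no power for it. The specimens are collected while the subject is already under anaesthesia for needle placement, the size is set by a morbidity rule whose figures reproduce, and the plan's only decision rests on that rule. The missing definition of prognosis is a gap that an analyst would fill by listing whatever events occur beside the molecular findings. Relabelling the aim would leave the sample size, data, analysis and decision rule exactly as they are.
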